Randomized Trial to Compare the SherpaPak™ Device vs Cold Storage of Donor Hearts in Transplantation: A Pilot Study

Version 3, February 16, 2022

Principal Investigator:
[name]
Surgical Director, Heart Transplant Program

Cedars-Sinai Medical Center

TABLE OF CONTENTS

Protocol Summary	3
General Information	3
Protocol Amendment History	3
1.0 BACKGROUND, RATIONALE	4
2.0 STUDY OBJECTIVES	4
3.0 STUDY POPULATION.....	5
3.1 Selection of the Study Population.....	5
3.2 Inclusion Criteria	5
3.3 Exclusion Criteria	5
3.4 Subject Screening and Enrollment.....	5
3.5 Subject Recruitment	6
4.0 STUDY DESIGN AND METHODS.....	6
4.1 Schedule of Procedures	7
5.0 DATA COLLECTION AND MANAGEMENT.....	7
5.1 Data Procurement	7
5.2 Time Period of Data Under Review	8
5.3 Variables Collected.....	8
5.4 Source Documents	9
5.5 Data Collection and Storage	9
5.6 Confidentiality and Security of Data.....	10
6.0 DATA AND SAFETY MONITORING.....	10
6.1 Data and Safety Monitoring Plan.....	10
6.2 Quality Control and Quality Assurance	12
7.0 STATISTICAL CONSIDERATIONS.....	13
7.1 Study Outcome Measures.....	13
7.2 Sample Size Considerations	13
8.0 REFERENCES	13

PROTOCOL SUMMARY

Purpose and Knowledge to be Gained	
The purpose the research is to compare the SherpaPak™ Cardiac Transport System to standard of care cold storage of donor hearts for transplantation.
 
Successful use of this device may decrease cold injury of donor hearts by maintaining the temperature consistently during transport and therefore may decrease primary graft dysfunction after transplantation.

Research Procedures	The primary research procedure is the use of the SherpaPak Cardiac Transport System for the preservation and transport of donor hearts for transplantation
Subject Population	Patients listed for heart transplant at Cedars-Sinai
Duration	
The study includes 6 visits.
 
The total study duration is 30 days

GENERAL INFORMATION

Sponsor/Funder	Internally Funded
Collaborating Institutions Involved in the Research	Not Applicable

PROTOCOL AMENDMENT HISTORY

Protocol Version	Summary of Changes/Rationale for Changes
Protocol V3: February 16, 2022	
 - Removed CSMC Co-Investigators section under General Information as this section would be too large - Section 3.3 Exclusion Criteria removed all exclusion criteria - Section 4.0 Study Design, Schedule of Procedures updated to add Randomization at Visit 1, extend the visit #6 window and clarify timing of biopsy tissue collection - Section 5.1 Data Procurement removal of AHD Registry language as this registry will not be utilized - Minor revisions throughout protocol for clarity - Section 6.0 Data Safety Monitoring, language regarding the DSMB Charter has been inserted - Formatting revised throughout
Initial Protocol V2: July 15, 2021	N/A

1.0 BACKGROUND, RATIONALE

Cardiac transplantation is currently the procedure of choice for selected patients with end-stage heart disease that is not amenable to further medical intervention or conventional cardiac procedures. Successful organ preservation is an important component of transplantation and ensures the maintenance of organ viability until implantation into the recipient. Currently, heart preservation for transplantation is limited to 4 to 6 hours of cold ischemic storage. Longer periods of ischemia are associated with poor outcomes post transplantation. In heart transplantation, preservation injury and ischemic reperfusion injury contribute to microvascular dysfunction and myocardial injury leading to primary graft dysfunction or to the activation of pro-inflammatory and pro-fibrotic processes, and the development of cardiac fibrosis and allograft vasculopathy.

In general, instructions for the use of organ preservation solutions state a temperature range of 2-8°C or 4-8°C, balancing the risk of cold injury at lower temperatures against the risk of hypoxic injury at higher temperatures. The standard method of storing donor hearts in preservation fluid within sequential bags that are then placed on ice and transported in a cooler does not allow for exact temperature control. The SherpaPak™ Cardiac Transport System has been developed to provide a safe, consistent method for cold ischemic storage of donor hearts for transplantation. Successful use of this device may decrease cold injury of donor hearts by maintaining the temperature consistently during transport and therefore may decrease primary graft dysfunction after transplantation.

2.0 STUDY OBJECTIVES

Primary Objective

To compare the SherpaPak™ Cardiac Transport System to standard of care cold storage of donor hearts for transplantation.

Secondary Objective

To assess for a decrease in cold injury of donor hearts and therefore a decrease in primary graft dysfunction. To assess for events between study groups.

Primary Endpoint

The primary endpoint will be a composite endpoint of: Absence of moderate to severe primary graft dysfunction per ISHLT grading scale (left or right ventricle) in the first 24 hours post transplantation, and 30-day patient survival, 30-day incidence of ischemic reperfusion injury on endomyocardial biopsies and changes in mitochondria function and quality (at donor heart harvesting, at the time just prior to donor heart implantation and at one-week post- heart transplantation).

Secondary Endpoints – To describe between the groups

1. Each individual component of the composite endpoint will be assessed.
2. Hemodynamic parameters including cardiac index, cardiac output, blood pressure, mean arterial pressure, pulmonary artery pressure, left atrial pressure, right atrial pressure, right

ventricular pressure, stroke volume and ejection fraction at 24 hours post-transplant

3. The number of inotropes/pressors at 24 hours post -transplant.
4. Incidence of acute cellular rejection in the first 30 days post heart transplantation.
5. Incidence of antibody mediated rejection in the first 30 days post heart transplantation.
6. Incidence of heart graft related Serious Adverse Events in the first 30 days post heart transplantation.
7. Total length of stay
8. ICU length of stay
9. Number of blood products used

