4.1 SCHEDULE OF PROCEDURES

Procedures/Assessments	Screening Visit	Visit 1 (Day 0 at Transplant)	Visit #2 (Day 7 post-transplant ± 2 days)	Visit #3 (Day 14 post-transplant ± 2 days)	Visit #4 (Day 21 post-transplant ± 2 days)	Visit #5 (at hospital discharge)	Visit #6 (Day 30 post-transplant ± 14 days)
Eligibility & Informed Consent	X						
Demographics/Characteristics	X						
Medical & Cardiac History	X						
Confirm Eligibility/Randomize		X					
Data Collection Donor Characteristics		X					
Patient Visit (recipient)	X	X	X	X	X	X	X
Tissue Collection for biopsy (donor heart prior to transport & prior to transplant)		X	X				
Mitochondrial Testing		X	X				
Data Collection Transplant Details		X					
Data Collection PGD Scores		X	X				X
Data Collection Inotrope Support		X	X			X	X
Right Heart Catheter Data		X					
Data Collection Mechanical Circulatory Support		X	X			X	X
Data Collection Invasive Ventilator Support		X	X				
Endomyocardial Biopsy (recipient)			X	X	X		X
Data Collection Patient Survival							X
Data Collection Graft Survival							X
Data Collection Post-Transplant Hemodynamics		X	X				X
Data Collection Immunosuppressive Meds & Induction (if applicable)		X	X			X	X
Data Collection ICU & Hospital Stay						X	
Data Collection Heart Graft-Related AEs and SAEs		X	X	X	X	X	X

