5.3 VARIABLES COLLECTED

The following data points/variables will be collected:

- Incidence of primary graft dysfunction
- Initial use of mechanical circulator support: The use of ECMO, intra-aortic balloon, LVAD, RVAD or biVAD
- Number of inotropes/pressors at 24 hours post-transplant
- Inotropic support for first 72 hours: The following inotropic medication doses will be collected at ICU admission T0, T12, T24, T48, and T72 hours after ICU admission post-heart transplantation:
 - Dopamine – mcg/kg/min
 - Dobutamine – mcg/kg/min
 - Amrinone – mcg/kg/min
 - Milrinone – mcg/kg/min
 - Epinephrine – mcg/kg/min
 - Norepinephrine – mcg/kg/min
- Initial use of mechanical respiratory support: Duration of initial post-transplant invasive ventilator support from time of initial admission to ICU post heart transplant until extubation
- Immunosuppression Medications (at day 7 and at time of discharge)
- Incidence of reperfusion injury on endomyocardial biopsy
- Cardiac index
- Cardiac output
- Blood pressure
- Mean arterial pressure
- Pulmonary artery pressure
- Pulmonary capillary wedge pressure
- Left atrial pressure
- Right atrial pressure
- Right ventricular pressure
- Stroke volume
- Ejection fraction
- BUN and Creatinine
- Liver function tests

- Cellular rejection
- Antibody mediated rejection
- Graft-related serious adverse events
- Mitochondrial function
- Age at transplant
- Sex
- Donor characteristics
- Total cross clamp duration in minutes
- Ischemic time
- Surgical complications
- Total length of stay
- ICU length of stay
- Total blood products used
- Trans-thoracic echocardiogram results prior to discharge:
 - Ejection Fraction (EF%)
 - Wall motion assessment
 - LV Septal and posterior wall thickness
 - Any valve abnormalities
- Patient and graft survival at day 30
- Incidence of acute cellular rejection in the first 30 days post heart transplant
- Incidence of antibody mediated rejection in the first 30 days post heart transplant
- Adverse events: All heart graft-related serious adverse events and any heart graft-related adverse events will be followed and documented until the investigator designates the event to be either resolved or its effect on the patient's condition stabilized.
- Medications: Medications used to treat all serious heart graft-related adverse events (SAEs) until the SAE is resolved.

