6.0 DATA AND SAFETY MONITORING

6.1 DATA AND SAFETY MONITORING PLAN

Safety will be analyzed principally by examination of the frequency of adverse events. In particular, the number of donor heart graft-related serious adverse events (SAEs) up to the 30-day follow-up after transplantation per subject will be analyzed. This endpoint is defined to consist of the following adverse events (at most one per type), if they are serious adverse events:

- Primary heart graft dysfunction (not including rejection or cardiac tamponade):
 - Use of ECMO, RVAD, LVAD, BiVAD or insertion of a new IABP for >12 hours post TX.
 - Use of ≥ 2 inotropic agents/vasopressors including high-dose epinephrine or norepinephrine for >7 days post heart TX.
 - Open chest post heart TX. due to compromised heart function
- Primary graft failure requiring re-transplantation

Subjects will be monitored before, during and after the operative procedure to help ensure their safety. The investigators are members of transplant teams who have extensive experience with heart transplants and who will be trained to use the SherpaPak Cardiac Transport System to further minimize risk.

Subjects in the trial will undergo frequent visits and routine monitoring to help detect any abnormal changes and to provide appropriate treatment as necessary.

An independent Data and Safety Monitoring Board (DSMB) comprised of two expert heart failure physicians and one cardiothoracic surgeon not participating in the trial, will perform

monitoring activities to ensure the identification, documentation, and analysis of adverse events; and to ensure compliance with the protocol and procedures that are in place for conducting research to protect the safety and well-being of all subjects. The DSMB will have a formal meeting at least once annually. Frequency of the meetings may be changed by the DSMB in consultation with the Principal Investigator based on need. An ad hoc meeting may be called at any time by the Chairperson or by the PI and research staff should ethical or patient safety issues arise.

A status update will also be provided to the DSMB on a quarterly basis via email correspondence by the DSMB Coordinator.

The criteria below provide guidance for suspending trial enrollment/randomization until review by the DSMB. Selected serious adverse events (SAEs) of concern and their thresholds are:

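### The survival component of the primary endpoint counts patients alive, not randomised hearts still in place, although graft survival at Day 30 is already collected

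*Combined protocol and SAP*

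**What the plan says.** Section 2.0 builds the primary endpoint from four components. The first concerns the graft and is limited in time: "Absence of moderate to severe primary graft dysfunction per ISHLT grading scale (left or right ventricle) in the first 24 hours post transplantation". The text then continues "and 30-day patient survival, 30-day incidence of ischemic reperfusion injury on endomyocardial biopsies", and ends with mitochondrial changes measured at harvest, just before implantation and "at one-week post- heart transplantation". No rule for combining the components is stated. Secondary endpoint 1 reports each component separately.

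Graft survival is not named among the primary or the nine secondary endpoints, but it is collected. Section 5.3 lists "Patient and graft survival at day 30", and the schedule in section 4.1 has a Visit 6 row, "Data Collection Graft Survival", separate from the row for patient survival.

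The protocol foresees loss of the heart. Section 6.1 includes "Primary graft failure requiring re-transplantation" among the event types of its safety endpoint. The matching efficacy-list entry is secondary endpoint 6, "Incidence of heart graft related Serious Adverse Events in the first 30 days post heart transplantation".

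Recipient biopsies are scheduled at Days 7, 14, 21 and 30 (section 4.1). Neither section 4 nor section 7 says how a re-transplanted subject, or tissue taken after re-transplantation, is to be handled.

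**The concern.** The unit on which the intervention acts is the donor heart. Section 1.0 justifies the trial by organ viability and reduced graft injury, so loss of the randomised heart is the most direct failure of preservation that the trial could observe. A survival component defined on the patient does not distinguish a subject whose preserved heart is working from one whose heart was lost and replaced.

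There is a related gap in the tissue results. After a replacement, any later biopsy samples a heart that was not the one randomised. If the replacement came before the one-week mitochondrial sample, that sample would be set against harvest and pre-implant samples from a different organ, and the difference would not be a change in either heart.

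In a pilot that is read descriptively, individual cases carry much of the interpretation, so it matters that each is classified as intended.

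**Working it through.** The plan gives no event rate, power or effect size for this endpoint, so there is no stated figure to reproduce. The check is a classification of cases followed by simple arithmetic.

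**Step 1. How a subject is classified under section 2.0 and under a graft-based definition.**

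| Course to Day 30 | PGD component | Patient survival (as written) | Survival with randomised graft |
|---|---|---|---|
| Alive, randomised heart in place, PGD no worse than mild in 24 h | success | success | success |
| Moderate or severe PGD within 24 h, re-transplanted, alive | failure | success | failure |
| No worse than mild PGD in 24 h, heart lost later, re-transplanted, alive | success | success | failure |
| Died | depends on grade | failure | failure |

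The survival component differs in the second and third rows. Only in the third row do both the PGD and survival components record success. What the whole composite records cannot be settled, because section 2.0 gives no combining rule.

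**Step 2. Size of one case.** Section 3.4 gives 1:1 allocation. Section 4.0 gives about 20 subjects, but its wording leaves open whether this is the total or the number per arm.

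- 20 in total, 10 per arm: 10/10 instead of 9/10, a shift of 1/10 = 10 percentage points.
- 20 per arm: 20/20 instead of 19/20, a shift of 1/20 = 5 percentage points.

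**Step 3. Chance that it arises at all.** The documents give no re-transplantation rate, so the rates p below are assumptions for scale only. The chance of at least one case among n subjects is 1 − (1 − p)^n.

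| Assumed 30-day rate | n = 20 | n = 40 |
|---|---|---|
| 1% | 1 − 0.99^20 = 18% | 33% |
| 2% | 33% | 55% |
| 3% | 46% | 70% |
| 5% | 64% | 87% |

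These figures are for any re-transplantation. The chance of a case that passes both components is smaller, because some of these subjects will already have failed on PGD.

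**Step 4. Tissue results.** Suppose reperfusion injury and rejection are counted once per subject over 30 days. A positive finding in the first heart then stays counted, and biopsies of the second heart can only add events compared with stopping at graft loss. If second-heart biopsies are instead dropped without comment, follow-up in the affected arm is shorter and its recorded incidence may fall. For mitochondrial change, nothing in the documents indicates a direction.

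**The case against.** The strongest reply is that the plan already looks at the graft. The composite opens with graft dysfunction in either ventricle. Re-transplantation for primary graft failure is a graft-related serious adverse event reported through secondary endpoint 6, and graft survival is collected on its own row. With about 20 subjects, a single replacement would be noticed. Patient survival is also a legitimate outcome, correctly labelled, and section 7.2 makes the comparison primarily descriptive, so no error rate is at stake.

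Most of this stands, and it limits the weight of the point. It does not remove it. The PGD component stops at 24 hours. Secondary endpoint 6 pools re-transplantation with device support, prolonged inotrope use and open chest, and it leaves the separately reported survival component unchanged.

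Three stronger readings are tempting and are not supported:

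- A reader might infer that the primary endpoint ignores the graft, or that graft loss goes unreported. Neither is so, for the reasons just given.
- A reader might infer that every resulting error flatters the arm that lost the heart. That holds for the survival component. As step 4 shows, it does not follow for biopsy, rejection or mitochondrial results.
- A reader might infer that the mitochondrial series will be mixed across hearts. Section 4.0 describes it as tissue from donor hearts at three times, which most naturally means one heart followed through. A mix-up requires a replacement before the Day 7 ± 2 sample. What is missing is an explicit rule.

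**Conclusion.** The point holds as a cheap improvement to the endpoint definition. As written, a subject re-transplanted within 30 days and alive is a success on the survival component. That subject is a success on PGD as well if the graft failed after 24 hours or graded no worse than mild within them. Each case shifts the survival component by 10 points with 10 per arm, or 5 points with 20 per arm. Whether any case occurs depends on a rate that the documents do not give and that is probably low. The effect is on interpretation; no test or sample-size calculation is affected. The handling of tissue from a replacement heart is unspecified, and the direction of any resulting bias cannot be determined from the documents.

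**What to change.** 1. In section 2.0, define the survival component as 30-day survival with the randomised graft, meaning alive without re-transplantation. Use the graft survival already collected at Visit 6, and report patient survival beside it.
2. State that mitochondrial samples are paired only within the randomised heart.
3. State that biopsy and rejection findings from a replacement heart are reported separately. Show graft loss by arm alongside the incidence of injury and rejection, so that shortened follow-up of a lost heart is not read as absence of injury. Simply excluding the later samples would not be enough.

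The cost is a few sentences in sections 2.0 and 7.1, with no new visits or data. The downside is that the reported survival rate may be slightly less favourable.

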3.0 STUDY POPULATION

3.1 SELECTION OF THE STUDY POPULATION

- Study subjects will be drawn from patients listed for heart transplant at Cedars-Sinai Medical Center.

3.2 INCLUSION CRITERIA

- Any sex/gender, 18 years of age or older listed for heart transplant.
- Subjects must be willing and be capable of understanding the purpose and risks of the study and must sign a statement of informed consent OR consent of a legally authorized representative of a cognitively impaired individual will be obtained before the cognitively impaired individual may be included in research.
- Signed: 1) written informed consent document and 2) authorization to use and disclose protected health information
- Subjects must receive and accept a non-local donor offer (from Northern California, Arizona, Nevada or farther geographies)

3.3 EXCLUSION CRITERIA

Not Applicable

3.4 SUBJECT SCREENING AND ENROLLMENT

All patients on the heart transplant waiting list at Cedars-Sinai will be identified by trial investigators and screened for trial eligibility. Those patients who initially appear eligible for the trial will have the trial thoroughly explained to them by a trial investigator, be invited to participate, and will be asked to sign an informed consent. Consent of a legally authorized representative of a cognitively impaired individual will be obtained before the cognitively impaired individual may be included in research.

When a matching donor heart becomes available, the inclusion and exclusion criteria will be re-verified by the study team. If the recipient is no longer eligible for the trial, they will be considered a screen failure and they will exit the study and no information will be collected for these patients.

If the subject is matched with a donor heart from a local donor (Southern California), the

subject will be considered a screen failure and they will exit the study and no information will be collected for these patients.

When a matching donor heart from a non-local donor offer (from Northern California, Arizona, Nevada or farther geographies) becomes available the recipient will be assigned a subject identification number and randomized 1:1 to receive a heart transported using either standard of care cold storage or the SherpaPak™ Cardiac Transport System. REDCap will be used for randomization.

3.5 SUBJECT RECRUITMENT

All subjects will be patients of the principal investigator and co-investigators, managed as part of the Cedars-Sinai Advanced Heart Failure/Heart Transplant Program. Subjects will be approached in person during clinic visits or upon hospital admission by investigators or study coordinators after confirming eligibility. No advertising will be used for recruitment purposes.

4.0 STUDY DESIGN AND METHODS

This study is designed to be conducted as a single-center randomized prospective trial to compare the SherpaPak™ Cardiac Transport System to standard of care cold storage for donor hearts in transplantation. Approximately 20 consented subjects will receive a donor heart transported using either cold storage or the SherpaPak™ Cardiac Transport System, respectively. Both methods are FDA approved.

Donor hearts will be screened for eligibility based on current standard of care criteria. Heart transplant candidates will be screened for trial eligibility. Every eligible candidate will be asked to participate. Eligible and consented transplant candidates will receive donor hearts transported using standard of care cold storage or the SherpaPak™ Cardiac Transport System, that have been deemed clinically acceptable for transplantation by the treating transplant clinical team.

The study will be evaluating the comparative use of two FDA-approved methods for organ procurement. The research procedures will be randomization, data collection/analysis, and tissue collection from standard of care biopsies for mitochondrial testing.

Mitochondrial Testing

Biopsy tissue from donor hearts will be collected prior to transport, prior to transplant and at one-week post-transplant. The tissue will be evaluated to detect changes in mitochondrial function and regulation.

Biopsy tissue will be processed and stored by the [name] Laboratory at Cedars-Sinai. The [name] Laboratory, led by [name], is studying the molecular mechanisms regulating mitochondria in the heart's response to ischemic injury.

